## 3.3.2. COVID-19 Related Endpoints

 Percentage of CAP events with pneumococcal infection identified by any means (e.g., UAD, BinaxNOW®, bacterial culture) among CAP events associated with a positive COVID-19 test compared to percentage of CAP events with pneumococcal infection identified by any means (e.g., UAD, BinaxNOW®, bacterial culture) among CAP events associated with a negative COVID-19 test, overall and stratified by age, sex, and pneumococcal risk status.

The following calculations will be made for overall and stratified by age group, sex, and pneumococcal risk status among COVID-19 subpopulation, i.e. all enrolled population with a valid results from COVID-19 viral pathogen testing.

 Among CAP subjects with COVID-19 infection, percentage of CAP subjects with severe clinical outcomes (overall and by individual outcome) among those with pneumococcal coinfection identified by any means (e.g., UAD, BinaxNOW®, bacterial culture) compared to percentage of CAP subjects with serious clinical outcomes among those without pneumococcal co-infection identified by any means (e.g., UAD, BinaxNOW®, bacterial culture), overall and stratified by age, sex, and pneumococcal risk status.

In this analysis, the patients with COVID-19 will be divided into two groups:

- those with coinfection with Sp identified by any means (e.g., UAD, Binax, bacterial culture).
- those without coinfection with Sp identified by any means (e.g., UAD, Binax, bacterial culture).

The definitions of the severe clinical outcomes are given below:

- Admitted at ICU: admission at ICU, irrespective of duration of ICU stay.
- PaO2/FiO2 ratio: PaO2/FiO2 ratio<250.

- Respiratory rate: respiratory rate>30 breaths/min.
- Outcome of illness: death.
- Use of mechanical ventilation: any type ventilation (intubation or non-invasive positive pressure).
- Diagnosed as Acute Respiratory Distress Syndrome (ARDS): diagnosis of ARDS.

DMB02-GSOP-RF02 5.0 Statistical Analysis Plan Template 05-Dec-2019
PFIZER CONFIDENTIAL
Page 13
TMF Doc ID: 98.03

- Any severe outcome: If the participant falls in any of the categories of severe clinical outcomes as described above, then the participant will fall in this category.
- VE calculated as 1 minus the OR comparing the odds of having received PCV13 by cases and controls, multiplied by 100%, overall and among immunocompetent persons only, adjusted for confounders. (Cases=COVID-19-positive CAP subjects with severe clinical outcomes; Controls=COVID-19-positive CAP subjects without severe clinical outcomes. This will be a nested case-control study, and the COVID-19 status will be determined from standard-of-care viral testing. The cases are CAP patients with COVID-19 with severe clinical outcomes, and the controls are the CAP patients with COVID-19 without severe clinical outcomes. Several clinical outcomes will be used in the definition of cases and
  - Patients admitted to the ICU

controls as stated below:

- Patients with PaO2/FiO2 ratio <250 mmHg

- Patients with respiratory rate >30 breaths/min
- Patients died
- Patients received mechanical ventilation
- Patients diagnosed as ARDS
- Any severe clinical outcome mentioned above
- Frequency of pneumococcal carriage among subjects with current/recent COVID-19 infection compared to frequencyof pneumococcal carriage among subjects without current/recent COVID-19 infection, overall and stratified by age, sex, and pneumococcal risk status.
  - In this analysis, the denominator will be the Saliva Carriage Subpopulation with COVID-19 status to be determined from standard-of-care viral testing.

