#### Concomitant Medications

- Influenza Vaccine History (in last year only)
- Vaccination History PPV23
- Vaccination History PCV13
- COVID-19 Marketed Vaccine History (COVID MRKT)
- COVID-19 Investigation Vaccine History (COVID INV)

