For the primary endpoint, the cases will be the patients with CAP in whom PCV13 serotypes are identified by any method and the controls will be the patients with CAP without having VT serotype (even the CAPs for which the serotype was not identified). Multivariable logistic regression model (Appendix 3.3), will be applied to estimate odds of exposure to PCV13 among cases versus controls. All VE estimates will be calculated as  $(1 - \text{odds ratio}) \times 100\%$ . Both unadjusted and adjusted VE will be estimated. Patients' age, sex, study site and the variables deemed to be potential confounders on the basis of prior knowledge (e.g. nationality to be modeled as Spanish vs. non-Spanish; risk level to be modeled as low vs. at-risk vs. high-risk; BMI category to be modeled as obese vs. overweight vs. normal vs. underweight; PSI score as continuous; current drug abuse; antibiotic use within past 14 days; influenza vaccination within the last year; pneumonia in last year [ordinal variable, 0,1,2,3] and PPV23 receipt in past 5 years) will be included in the multivariable regression model for adjustment. Initially, we will employ bivariate models, and only the variables significant at p<.20 in the bivariate models will be included in the final model for adjustment.

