## Variables to be used to calculate the propensity scores

Variables for calculating the propensity score.

- Patients' age: continuous
- Sex: female=0, male=1
- Nationality: Spanish=0, non-Spanish=1
- Risk level: low-risk=0, at-risk=1, high-risk=2
- PSI score: continuous
- Antibiotic use within past 14 days: no=0, yes=1)
- Influenza vaccination within past one year: yes=0, no=1
- Pneumonia in the last year: ordinal value=0, 1,2,3
- Season of admission: Spring (Mar-May)=0, Summer (Jun-Aug)=1, Autumn (sep-Nov)=2, Winter (Dec-Feb)=3.
- PPV23 receipt in past 5 years: yes=0, no=1
- CAP event occurrence during COVID-19 pandemic: 0=not during COVID-19, 1=During COVID-19 (The study is started in the pandemic period; the variable will be used if we find a non-pandemic period during the study period)

The study site will be exactly matched. Note that the categorical variable will be put in the model like the ordinal values.

The conditional logistic regression will be employed to estimate odds of exposure to PCV13 among these matched cases and controls. The VE estimate will be calculated as  $(1 - \text{odds ratio}) \times 100\%$ . We will use a two-sided alpha of 0.05 for all analyses.

In the 2nd sensitivity analysis (PPV23 Naïve population), the cases will be the hospitalized CAP in whom PCV13 serotypes are identified by any method and had not received PPV23 in the last five years from the date of visit; the controls (also PPV23 Naïve population), will be selected using the propensity score matching as described above. A conditional logistic regression will be employed to estimate odds of exposure to PCV13 among cases versus controls in the PPV23 naïve population. The VE estimate will be calculated as (1 – odds ratio) × 100%. We will use a two-sided alpha of 0.05 for all analyses.

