## 6.3.7.1. COVID-19 Related Endpoint 3 - Main Analysis

In this analysis:

- The cases are CAP cases with COVID-19 with severe clinical outcomes
- The controls are CAP cases with COVID-19 without severe clinical outcomes

The controls will be selected by matching by the propensity score as described above. We will then develop six models as follows:

Model 1: Cases: COVID-19+ve with any severe outcome; Controls: COVID-19+ve without a severe outcome

Model 2: Cases: COVID-19+ve and admitted to ICU; Controls: COVID-19+ve and not admitted to ICU

Model 3 : Cases: COVID-19+ve and PaO2/FiO2 ratio <250 mmHg; Controls: COVID-19+ve and PaO2/FiO2 ratio ≥250 mmHg

Model 4: Cases: COVID-19+ve and Respiratory rate >30 breaths/min; Controls: COVID-19+ve and Respiratory rate ≤30 breaths/min

Model 5: Cases: COVID-19+ve and died; Controls: COVID-19+ve and alive.

DMB02-GSOP-RF02 5.0 Statistical Analysis Plan Template 05-Dec-2019
PFIZER CONFIDENTIAL
Page 40
TMF Doc ID: 98.03

Model 6: Cases: COVID-19+ve and received mechanical ventilation; Controls: COVID-19+ve and did not receive mechanical ventilation

Model 7: Cases: COVID-19+ve and diagnosed as ARDS; Controls: COVID-19+ve and not diagnosed as ARDS

For each of the models, we will employ a conditional logistic regression model and will estimate odds of exposure to PCV13 among cases versus controls. The VE estimate will be calculated as (1 – odds ratio) × 100%. We will use a two-sided alpha of 0.05 for all analyses.

These models will also be replicated for immunocompetent (absence of immunocompromising conditions, i.e., high-risk conditions) persons only.

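### The exploratory PCV13 effectiveness against severe COVID-19 reuses a propensity score that omits COVID-19 vaccination and BMI, although both are recorded

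*SAP*

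**What the plan says.** Protocol section 8 and SAP 3.3.2 define an exploratory endpoint: PCV13 VE against severe outcomes among COVID-19-positive CAP patients, "overall and among immunocompetent persons only, adjusted for confounders". Neither place names the confounders. Protocol 12.4.3 leaves the COVID-19 methods to the SAP.

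SAP 6.3.7.1 carries out the adjustment in two steps:

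- "The controls will be selected by matching by the propensity score as described above".
- For each of Models 1 to 7, "we will employ a conditional logistic regression model and will estimate odds of exposure to PCV13 among cases versus controls". No covariates are named.

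The score in question is the list in SAP 6.1.1.2 headed "Variables for calculating the propensity score". It was written for the sensitivity analyses of vaccine-type pneumonia. It holds age, sex, nationality, risk level, PSI score, recent antibiotics, influenza vaccination, pneumonia in the last year, season, PPV23 in the past five years and a pandemic-period indicator that is used only if a non-pandemic period occurs. In addition, "The study site will be exactly matched".

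COVID-19 vaccination and BMI are not on the list. Both are collected at Visit 1 (Protocol 10.3), COVID-19 vaccination with dates and product types. SAP 3.4 lists COVID-19 vaccine history as a baseline variable, but no VE model uses it. BMI is a candidate confounder in the primary model of SAP 6.1.1.1: "BMI category to be modeled as obese vs. overweight vs. normal vs. underweight".

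**The concern.** The score was assembled for a different outcome. In Models 1 to 7 every case and every control is COVID-19-positive and the outcome is severity, so COVID-19 vaccination is a direct determinant of the outcome. It confounds the PCV13 estimate if it also tracks PCV13 receipt.

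The documents make such a link plausible. Protocol section 7 says that adult pneumococcal vaccination is mostly given during influenza campaigns, and Protocol 9.1 accepts that healthy-vaccinee effects can leave residual confounding. The only COVID-related item in the score is a calendar-period flag, which says nothing about a patient's own vaccination.

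At stake is an estimate that would be reported as adjusted while leaving out a recorded variable that a reader would expect to see first. With more COVID-19 vaccination among PCV13 recipients, part of the benefit of the COVID-19 vaccine would be credited to PCV13.

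**Working it through.** The documents give no sample size, effect size or uptake figure for this endpoint, so there is no stated figure to reproduce. **All inputs below are assumptions**, and the true PCV13 effect is set to zero throughout.

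**1. No other adjustment.** Let r0 be the risk of a severe outcome without COVID-19 vaccination, θ the odds ratio of COVID-19 vaccination for a severe outcome, and c the COVID-19 vaccine uptake in a PCV13 group.

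- Odds in the COVID-19-vaccinated = θ × r0/(1 − r0), which gives their risk r1.
- Risk in a PCV13 group: R = c × r1 + (1 − c) × r0.
- Spurious VE = 1 − [R₊/(1 − R₊)] / [R₋/(1 − R₋)], with + for PCV13 recipients and − for non-recipients.

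With r0 = 40%:

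| Uptake, PCV13+ vs PCV13− | θ | r1 | R₊ | R₋ | Spurious VE |
|---|---|---|---|---|---|
| 90% vs 80% | 0.7 | 0.318 | 0.326 | 0.335 | 3.6% |
| 90% vs 80% | 0.5 | 0.250 | 0.265 | 0.280 | 7.3% |
| 90% vs 70% | 0.3 | 0.167 | 0.190 | 0.237 | 24.3% |

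Middle row in full: odds 0.265/0.735 = 0.3605 and 0.280/0.720 = 0.3889; ratio 0.927; VE 7.3%.

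The size of the uptake gap matters most. With r0 = 30%:

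| Uptake | θ = 0.5 | θ = 0.3 |
|---|---|---|
| 95% vs 90% | 4.0% | 8.0% |
| 95% vs 85% | 7.8% | 15.0% |
| 95% vs 80% | 11.3% | 21.1% |

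Moving r0 to 20% or 40% changes these by less than 2 points.

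**2. With part of the planned adjustment.** One simulated data set of 400,000 patients had 15.7% PCV13 coverage and COVID-19 uptake of 92.1% in recipients against 84.1% in non-recipients, with both vaccines driven by a common tendency to accept vaccination. Obesity had 30% prevalence and odds ratio 1.8, unrelated to PCV13. Ordinary logistic regression gave these apparent VEs:

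| θ | Unadjusted | Age, risk level, influenza vaccination | Plus COVID-19 vaccination and obesity |
|---|---|---|---|
| 0.5 | 3.3% | 5.9% | 1.3% |
| 0.3 | 7.6% | 9.4% | 1.2% |
| 0.2 | 10.8% | 11.6% | 0.0% |

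Simulation error is about 1 point: 62,800 PCV13 recipients with 25.5% severe give 1/√(62,800 × 0.255 × 0.745) ≈ 0.009 on the log-odds scale. The last column is therefore close to zero.

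The unadjusted column is lower than the middle one because simulated PCV13 recipients carry more risk conditions, which hides part of the bias until risk level is adjusted for.

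The two sets of figures also rest on different gaps: 10 to 20 points in the first table, 8 in the simulation. Putting the simulated uptakes into the formula with r0 = 40% gives 5.9% (θ = 0.5) and 11.2% (θ = 0.3), close to the middle column. The lower range after adjustment thus owes more to the smaller gap than to influenza vaccination as a proxy.

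**3. BMI alone**, by the same formula (r0 = 30%, obesity odds ratio 1.5 to 2):

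- Obesity 25% in recipients against 30–35% in non-recipients: spurious VE +2% to +7%.
- Equal prevalence: 0%.
- Obesity 35% in recipients against 25–30% in non-recipients: −2% to −7%.

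**The case against.** **The score already holds a proxy.** It includes "Influenza vaccination within past one year: yes=0, no=1", together with age, risk level, PPV23 and exact matching on site. A crude range of 4–24% is therefore not the bias of the planned estimate. This stands as to the 24%. It does not remove the point, because the simulation with influenza vaccination adjusted for still left 6–9%. That simulation used regression rather than matching and left out PSI, PPV23, season and site, so it is a guide only.

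**The direction is not established.** The documents give no COVID-19 vaccine uptake by PCV13 status. The protocol summary also says that PCV13 recipients aged 60 and over are enriched for risk factors. Residual confounding of that kind within a three-level risk variable would pull VE down. This stands: the upward direction is conditional on an uptake gap, and the net direction is unknown.

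**BMI adds little.** Its bias can take either sign, and in SAP 6.1.1.1 it enters only if it passes the p<.20 screen. This stands.

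**The endpoint carries little weight.** It is exploratory, it is run only if COVID-19 is frequent enough (Protocol 12.4.3), and SAP 5.1 sets no hypothesis test. For illustration, assume 300 COVID-19-positive patients, 35% severe, and 15% PCV13 coverage (the SAP 2.2 planning value). Then SE(log OR) = √(1/15.75 + 1/89.25 + 1/29.25 + 1/165.75) ≈ 0.34, and a null result has a 95% interval for VE of roughly −94% to +49%. A 7% shift is about 0.2 SE. This limits the priority but does not make the stated adjustment adequate.

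**Another section might repair it.** SAP Appendix 3.3 describes covariate selection for a multivariable logistic model. It is cited for the primary analysis, does not name COVID-19 vaccination, and is not the model used in 6.3.7.1.

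**Conclusion.** The gap is real. The plan promises an adjusted estimate, and its only stated adjustment omits a recorded, direct determinant of COVID-19 severity. If COVID-19 vaccination is more common in PCV13 recipients, Models 1 to 7 would show some spurious protection: about 4–24% with no other adjustment, and about 6–9% after adjustment for age, risk level and influenza vaccination (COVID-19 vaccine odds ratio 0.5 to 0.3). A smaller gap gives less. Every input is assumed.

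A reader might infer that the plan is bound to show false protection, that this could reach 24% in the planned estimate, or that omitting BMI pushes the same way. The documents support none of these: they give no uptake gap, the 24% ignores the matching, and BMI bias has no fixed sign. Nor does the point reach the primary VE, which concerns a different outcome and uses a separate model.

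**What to change.** Give SAP 6.3.7.1 its own adjustment set instead of a reference back to 6.1.1.2:

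- Add COVID-19 vaccination before admission, as number of doses and time since last dose. Fix the categories, including one for no dose, before outcomes are tabulated by PCV13 status.
- Add BMI category (SAP Appendix 2.2) as a further covariate.
- State whether these enter the propensity score or each conditional logistic model. The score is the safer place if severe outcomes are few.
- State a rule for missing values, such as a missing category. Under SAP 5.3, patients without height or weight would otherwise drop out of the analysis, and the documents do not say how many that is.
- Reconsider PSI in this score. Its elements in Protocol 10.3 include PaO2 or SpO2 with FiO2. These overlap the PaO2/FiO2 outcome of Model 3 and, through it, the composite in Model 1, so matching on PSI partly conditions on the outcome.

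The cost is SAP wording and some programming. No new data are needed.

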## 3.3.3. Additional RSV Exploratory Endpoints

 Proportion of CAP events where RSV was identified from saliva by PCR divided by all CAP events where the subject had a valid saliva specimen test result. If we have any other viruses detected within the scope of this study, then we will also describe those viruses.

DMB02-GSOP-RF02 5.0 Statistical Analysis Plan Template 05-Dec-2019
PFIZER CONFIDENTIAL
Page 14
TMF Doc ID: 98.03

The denominator for this endpoint will be the CAP population for which a valid saliva specimen test results from PCR is available.

## 3.4. Baselines Variables

## Demography

- Birth date
- Sex
- Nationality
- Enrolled previously in the current study.

## Disposition – Screening

- Date of Completion/Discontinuation/Death
- Status (Completed, Physician decision, Screen Failure, Withdrawal by Subject, Death, Other)
- Will the subject continue to the next phase of this study?

## Pre-Specified Significant Medical History

## High-risk (immunocompromised)

- Asplenia
- Cancer/Malignancy, Hematologic
- Cancer/Malignancy, Solid Tumor
- Chronic Kidney Disease
- Human Immunodeficiency Virus (HIV) AIDS
- Human Immunodeficiency Virus (HIV) No AIDS
- Immunodeficiency
- Immunosuppressant Drug Therapy
- Organ Transplantation
- Multiple Myeloma

DMB02-GSOP-RF02 5.0 Statistical Analysis Plan Template 05-Dec-2019
PFIZER CONFIDENTIAL
Page 15
TMF Doc ID: 98.03

#### At Risk (immunocompetent)

- Asthma
- Alcoholism
- Celiac Disease
- Chronic Liver Disease without Hepatic Failure
- Chronic Liver Disease with Hepatic Failure
- Chronic Obstructive Pulmonary Disease
- Cochlear Implant
- Congestive Heart Failure
- Coronary Artery Disease (CAD)
- Chronic Neurologic Diseases
- Coagulation factor replacement therapy
- CSF Leak
- Diabetes Treated with Medication
- Down syndrome
- Institutionalized in nursing home or LTC facility (Nursing home or long-term care facility for those with disability or dependency on subject characteristics/risk determinants eCRF page)
- Occupational risk with exposure to metal fumes
- Other Chronic Heart Disease
- Other Chronic Lung Disease
- Other pneumococcal disease risk factors
- Previous Invasive Pneumococcal Disease
- Tobacco smoking (Tobacco/E-Cigarettes)

The details of the pneumococcal risk classifications have been provided in Appendix 2.4.

DMB02-GSOP-RF02 5.0 Statistical Analysis Plan Template 05-Dec-2019
PFIZER CONFIDENTIAL
Page 16
TMF Doc ID: 98.03

## Subject Characteristics - Risk Determinants

- Where do you currently live?
  - Nursing Home [at risk-immunocompetent]
  - Private Residence
  - Long-term Care Facility for those with Disability or Dependency [at risk immunocompetent]
  - Other
- Healthcare Facility Exposure in the past 3 months
- Weekly exposure to children less than 5 years of age
- Antibiotics Used treatment within 14 days prior to admission
- Mental Status (confused/not confused)

## Substance Use

#### At Risk (immunocompetent)

- Tobacco (current user)
- E-cigarettes (current user)

## Not classified as risk

- Recreational Marijuana
- Illicit Drugs, not specified

#### Concomitant Medications

- Influenza Vaccine History (in last year only)
- Vaccination History PPV23
- Vaccination History PCV13
- COVID-19 Marketed Vaccine History (COVID MRKT)
- COVID-19 Investigation Vaccine History (COVID INV)

## Vital Signs

- Weight (kg)
- Height (cm)

DMB02-GSOP-RF02 5.0 Statistical Analysis Plan Template 05-Dec-2019
PFIZER CONFIDENTIAL
Page 17
TMF Doc ID: 98.03

- Systolic
- Diastolic
- Heart Rate
- Respiratory Rate
- Temperature (Celsius)
- SpO2 pulse oximetry percentage
- CRB-65 Score will be derived using the following elements:

Clinical factor	Point
Mental status is confused	1
Respiratory rate >30 breaths per minute	1
Systolic blood pressure <90 mm Hg or	1
Diastolic blood pressure ≤60 mm Hg	
Age ≥65 years	1

Charlson Co-morbidity index will be calculated using the table given in Appendix 6.

#### Oxygenation Parameters

- Date of assessment
- FiO2 (Fraction of Inhaled Oxygen)
- PaO2 (Arterial Blood Gases) will be derived from SpO2 as shown in Appendix 5. Note
  that if the timing of measurement for FiO2 and SpO2 are not same then PaO2 will
  not be calculated and will be treated as missing.

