 - COVID-19 vaccination, dates and vaccines types.
 - RSV vaccination, dates and vaccine types.
- Hospitalisation data:
 - Dates and time of admission/discharge for qualifying admission.
 - ICU stay (yes/no).
 - Number of days in ICU.
 - Mechanical ventilatory support (invasive and non-invasive), if used and type.
 - Number of days of mechanical ventilator use.
 - Acute respiratory distress syndrome (ARDS) diagnosis during illness.

PFIZER CONFIDENTIAL CT45-GSOP-RF152.0 Low-Interventional Study Protocol Template 05-Dec-2019 Page 36 of 70

- Readmission within 14 days of discharge (If yes, dates of admission/discharge).
- Symptoms of qualifying pneumonia illness mentioned in inclusion criteria.
- Date of illness onset.
- Vital signs (initial respiratory rate, pulse oximetry, blood pressure, heart rate).
- Level of oxygen supplementation during pulse oximetry measurement (FiO2).
- SOC chest radiography results (eg, CXR and computed tomography [CT] scan), including if consistent with pneumonia per standard outlined in Section 11.3.
- SOC microbiology test results including test and specimen type:
 - Blood cultures.
 - Respiratory microbiology testing, including bacterial (eg, PCR and culture), viral testing (eg, RSV, influenza, and COVID-19), and Gram stain results.
 - All standard –of care COVID-19 testing during the qualifying illness will be recorded with result.
 - Pneumococcal testing (eg, *BinaxNOW*[®] or another pneumococcal antigen urine test).
 - Other body fluid/tissue sterile under normal conditions.
- CAP severity/prognosis scale (Confusion Respiratory Rate Blood Pressure [CRB-65] and Pneumonia Severity Index [PSI]) on presentation to hospital if information available from SOC testing to calculate score:
 - CRB-65 score [Contributing data elements: age, blood pressure, presence of confusion, and respiratory rate].
 - PSI score. Contributing data elements are:
 - Altered mental status.
 - Nursing home residency.
 - pH and partial pressure of arterial O2 (PaO2) from atrial blood or arterialised venous blood OR oxygen saturation level (SpO2) measured by pulse oximetry

PFIZER CONFIDENTIAL CT45-GSOP-RF152.0 Low-Interventional Study Protocol Template 05-Dec-2019 Page 37 of 70

and FiO2 during that assessment.

- Blood urea nitrogen.
- Serum sodium concentration.
- Plasma glucose concentration.
- Hematocrit.
- Presence of pleural effusion.
- Relevant medical history:
 - COPD.
 - Asthma.
 - Congestive Heart Failure.
 - Coronary Artery Disease (CAD).

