Appendix 5: Conversion SaO2/PaO2

SpO2 (%)	Calculated PaO 2 (mmHg)
80	44
81	4 5
82	4 6
83	4 7
84	49
85	50
86	52
87	53
88	55
89	57
90	60
91	62
92	65
93	69
94	73
95	79
96	86
97	96
98	112
99	145

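### SpO2 below 80% or equal to 100% has no row in the SAP's PaO2 conversion table, so patients whose PaO2/FiO2 class that table already settles drop out of exploratory COVID-19 analyses

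*SAP*

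**What the plan says.** Under Oxygenation Parameters, SAP section 3.4 says that "PaO2 (Arterial Blood Gases) will be derived from SpO2 as shown in Appendix 5". It makes no exception for a measured value. The only stated route to a missing PaO2 is a difference in timing between the FiO2 and SpO2 measurements.

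The table, headed "Appendix 5: Conversion SaO2/PaO2", runs from 80% (44 mmHg) to 99% (145 mmHg). It has no row below 80%, none for 100%, and no rule for values outside its range.

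The protocol lists measured PaO2 among the elements of the severity score, if standard care supplies it. Section 10.3 names "pH and partial pressure of arterial O2 (PaO2) from atrial blood or arterialised venous blood OR oxygen saturation level (SpO2) measured by pulse oximetry", with FiO2 at that assessment.

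The ratio is used as an outcome in three places:

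- SAP 3.3.2 and 6.3.6.1: a ratio below 250 is one of six severe clinical outcomes compared between COVID-19 patients with and without pneumococcal co-infection.
- SAP 6.3.7.1, Model 3: "Cases: COVID-19+ve and PaO2/FiO2 ratio <250 mmHg; Controls: COVID-19+ve and PaO2/FiO2 ratio ≥250 mmHg".
- The composite of any severe outcome, which applies "If the participant falls in any of the categories of severe clinical outcomes as described above". It defines the cases of Model 1. No rule covers a limb that cannot be evaluated.

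SAP 5.3 sets the general rule: a participant with missing data is left out of the analysis that needs those data, and of no other.

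**The concern.** Whether the ratio can be derived depends on the quantity that defines the outcome. A very low SpO2 is itself evidence of a low ratio, yet it is the low end that the table leaves out. Known cases would leave Model 3, and known severe outcomes would leave the comparison in 6.3.6.

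What is at stake is the proportion severe by this criterion and the comparison by co-infection, if the loss differs between the groups. The Model 3 odds ratio is also exposed, if PCV13 coverage differs between the lost and the retained cases. In Model 1, two programmers could build different control groups from the same text.

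**Working it through.** The plan gives no figure to reproduce here. The check takes the table and the cut-off as written and asks what they imply outside the tabulated range.

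**Inputs**

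- PaO2 by SpO2: SAP Appendix 5.
- Cut-off: 250 mmHg (SAP 3.3.2 and 6.3.7.1).
- Room-air FiO2 of 0.21: an assumption, not given in the documents.
- PaO2 does not fall as SpO2 rises. This holds across the table and is assumed to continue beyond both ends.

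**Formula.** Ratio = PaO2 / FiO2. A tabulated PaO2 gives a ratio below 250 when FiO2 exceeds PaO2/250.

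**Low end.** SpO2 below 80% implies PaO2 of at most 44 mmHg.

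- On room air the ratio is at most 44/0.21 = 209.5. Any higher FiO2 makes it lower.
- The class would be in doubt only at FiO2 of 44/250 = 0.176 or less, which is below room air.
- So every SpO2 below 80% is under 250, and no FiO2 reading is needed to know it.

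**High end.** SpO2 of 100% implies PaO2 of at least 145 mmHg.

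- 145/250 = 0.58. For FiO2 up to 0.58 the ratio is at least 250.
- Above 0.58 the table cannot settle the class.

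**Inside the table.** Values are classed normally, including for patients on oxygen:

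| SpO2 | PaO2 (mmHg) | FiO2 | Ratio | Class |
|---|---|---|---|---|
| 86% | 52 | 0.21 | 247.6 | below 250 |
| 87% | 53 | 0.21 | 252.4 | 250 or above |
| 93% | 69 | 0.28 | 246 | below 250 |
| 97% | 96 | 0.40 | 240 | below 250 |
| 99% | 145 | 0.60 | 242 | below 250 |

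**Where an underivable ratio leads**

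1. Model 3: a control needs a ratio of at least 250, so a patient without a ratio is neither case nor control. SAP 5.3 removes the patient. With SpO2 below 80%, a known case is lost.
2. The PaO2/FiO2 outcome in 6.3.6: SAP 5.3 removes the patient in the same way.
3. The composite and Model 1: the patient is a case if any other limb is met (ICU admission, respiratory rate above 30, death, mechanical ventilation, ARDS). If none is met, the wording of 3.3.2 and 6.3.7.1 taken alone makes the patient a control, while SAP 5.3 excludes the patient. The SAP does not choose.

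**The case against.** Several points limit the concern, and most of them stand.

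- **A reader might infer that the most hypoxaemic patients as a class are lost.** The documents do not support that. Patients on oxygen with SpO2 of 80% to 99% and matched times get a ratio and are classed as severe where it is below 250, as the table above shows. Only SpO2 below 80% or at 100% lacks a row.
- **A reader might infer that patients without a ratio are counted as non-severe.** No rule says so. In Model 3 it cannot happen. In the composite it is one of two readings, and it needs all five other limbs to be negative.
- **A reader might call the table unstable near the top.** At FiO2 0.50, SpO2 98% gives 112/0.50 = 224 and 99% gives 145/0.50 = 290. That is a steep step in a coarse table. The documents hold no reference standard by which to call either class wrong, and the fix below would not remove the step.
- **The timing rule is partly met at collection.** Protocol 10.3 records the oxygen level during pulse oximetry, so FiO2 and SpO2 are meant to be paired.
- **Using measured PaO2 is not free of difficulty.** The protocol ties FiO2 to oximetry and lists no FiO2 paired with a blood gas. Blood gases in standard care are probably taken selectively, so mixing sources could make the method of measurement depend on severity.
- **The missing status of SpO2 below 80% is inferred.** The SAP does not state it. It follows from a derivation rule without exceptions and a table without the row.

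None of this answers the low end: followed as written, the plan cannot class patients whose class its own table fixes.

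**Conclusion.** The point holds and is minor. Patients with SpO2 below 80% drop out of Model 3 and of the PaO2/FiO2 outcome in 6.3.6, although all are below 250 (at most 209.5). Patients with SpO2 of 100% and FiO2 up to 0.58 drop out although they are at or above 250. A measured PaO2 has no stated role in the ratio, and the handling of a missing limb in the composite is open.

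The conclusion rests on FiO2 of at least 0.21 and on PaO2 rising with SpO2 beyond the table's ends. The documents give no SpO2 distribution, so neither the number of patients nor the size or direction of any bias can be computed. The ratio is an outcome only in exploratory COVID-19 endpoints 2 and 3, which Protocol 9.1 and 12.4.3 make conditional on sufficient COVID-19 frequency. The primary vaccine effectiveness analysis does not use it as an outcome.

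**What to change.** In SAP 3.4, for the analysis only:

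- (a) Classify SpO2 below 80% as PaO2/FiO2 below 250. State that this needs no time-matched FiO2, because the bound holds at every FiO2 from 0.21 up.
- (b) Classify SpO2 100% with a matched FiO2 of 0.58 or less as at or above 250. Otherwise leave the ratio missing.
- (c) Where a measured arterial PaO2 and an FiO2 from the same time are recorded, use them in place of the derived value. Otherwise use Appendix 5. Report the number of ratios by source.

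In SAP 3.3.2, with a reference in 6.3.6.1 and 6.3.7.1, state how a missing limb enters the composite. Report patients with a missing ratio and no positive limb both ways, excluded and counted as non-severe, as a sensitivity analysis. Exclusion should not be the only rule: it removes only possible non-cases and so raises the proportion severe.

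The cost is a few sentences and a few lines of derivation code. Rules (a) and (b) need no new data. Rule (c) applies only where a paired FiO2 exists, and it brings two sources of PaO2 into one variable, which is why the source should be reported.
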